2.4.2 Sample Size Calculation – Non-Repairable Cohort

The sample size, for the Non-repairable cohort, is determined based on the primary endpoint of freedom from all-cause mortality and heart failure hospitalization at 12 months.

The null and alternative hypotheses are stated in Section 2.3.2.1.

2.4.3 Sample Size Calculation – Severe MAC Cohort

The sample size, for the Severe MAC Cohort, is determined based on the primary endpoint of freedom from all-cause mortality and heart failure hospitalizations (HFH) at 12 months.

The null and alternative hypotheses are stated in Section 2.3.3.1.

Statistical Analysis Plan

2.5 Interim Analysis

No interim analysis is planned for this study.

2.6 Timing of the Analysis

The analysis of the primary endpoints and secondary endpoints of the Randomized, Non-repairable and Severe MAC Cohorts will be assessed when all registered subjects in the corresponding cohorts complete 12 months of follow-up.

2.7 Trial Success

2.7.1 Trial Success - Randomized Cohort

The Randomized Cohort will be considered successful if the primary composite endpoint meets non-inferiority test. Additional labeling claims may be made based on the secondary endpoints.

2.7.2 Trial Success - Non-Repairable Cohort

The Non-repairable Cohort will be considered successful if the primary composite endpoint meets the pre-specified performance goal. Additional labeling claims may be made based on the secondary endpoints.

2.7.3 Trial Success - Severe MAC Cohort

The Severe MAC Cohort will be considered successful if the primary endpoint meets the pre-specified performance goal. Additional labeling claims may be made based on the secondary endpoints.

2.8 Subgroups for Analysis

For a comprehensive understanding of the device performance and safety profile in specific subgroups, the following subgroup analyses of the primary endpoint are planned:

- Age: \geq Median baseline age, $<$ Median baseline age,
- Sex: Male, Female
- Baseline NYHA: II, III/IV

Statistical Analysis Plan

- Etiology of Heart Failure: Ischemic, Non-ischemic
- MR Etiology: Primary MR, Secondary MR

[REDACTED]

2.8.1 Subgroup Analysis – Randomized Cohort

[REDACTED]

2.8.2 Subgroup Analysis – Non-Repairable Cohort

[REDACTED]

2.8.3 Subgroup Analysis – Severe MAC Cohort

[REDACTED]

[REDACTED]

[REDACTED]

2.9 Handling of Missing Data

Analysis will be performed on all evaluable data.

[REDACTED]

[REDACTED]

[REDACTED]

2.10 Poolability Issue

All analyses will be performed by pooling data across study sites for the Randomized, Non-repairable and

[REDACTED]

[REDACTED]

Statistical Analysis Plan

Severe MAC Cohorts, respectively. Analysis will be conducted within each cohort to assess poolability of the primary endpoint across clinical trial sites.

2.11 Multiplicity Issues

The SUMMIT trial will be considered as three independent Cohorts: a Randomized cohort, a Non-repairable cohort and a Severe MAC Cohort. There is no multiplicity adjustment among the three cohorts.

2.11.1 Multiplicity – Randomized Cohort

For the Randomized cohort, hypothesis testing is planned for one primary endpoint and five secondary endpoints. If the primary endpoint is met, secondary endpoints will be evaluated for labeling claims. The first two and the group of the last three secondary endpoints will each be tested at the one-sided significance level of 2.5% and sequentially in the following order:

Statistical Analysis Plan

2.11.2 Multiplicity – Non-Repairable Cohort

For the Non-repairable Cohort, hypothesis testing is planned for one primary endpoint and five secondary endpoints. If the primary endpoint is met, the secondary endpoints will be evaluated for labeling claims. The five secondary endpoints will each be tested sequentially, as described in Section 2.3.2.2 above, in the following order:

1. Improvement in KCCQ at 12 months from baseline
2. Proportion of NYHA Functional Classification of I or II at 12 months
3. Improvement in Six-Minute Walk Test Distance at 12 months from baseline
4. Improvement in KCCQ at 6 months from baseline
5. Improvement in Six-Minute Walk Test Distance at 6 months from baseline

Statistical Analysis Plan

2.11.3 Multiplicity – Severe MAC Cohort

For the Severe MAC Cohort, hypothesis testing is planned for one primary endpoint and six secondary endpoints. If the primary endpoint is met, secondary endpoints will be evaluated for labeling claims. The six secondary endpoints will each be tested sequentially, as described in Section 2.3.3.2 above, in the following order:

1. Freedom from MR > mild (1+) at 30 days post index procedure
2. Improvement in KCCQ at 12 months from baseline
3. Proportion of NYHA Functional Classification of I or II at 12 months
4. Improvement in Six-Minute Walk Test Distance at 12 months from baseline
5. Improvement in KCCQ at 6 months from baseline
6. Improvement in Six-Minute Walk Test Distance at 6 months from baseline

[figure not shown]
2.12 Adjustment for Covariates

Unless otherwise specified, no adjustments for covariates will be made for any of the variables in the analysis.

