### **2.1.5 Transcatheter Edge-to-Edge Mitral Valve Repair (TEER)**

Transcatheter mitral valve repair techniques have been developed with the aim of providing lower-risk therapies to improve MR-related mortality and morbidity, and to expand treatment options for patients who are not good surgical candidates. The leading system for transcatheter mitral valve repair is the MitraClip, which performs edge-to-edge repair. The MitraClip device has been evaluated in multiple feasibility studies in various patient cohorts [13], [16], [18], [62], in RCTs against MV repair surgery [12], [15] and guideline-directed medical therapy (GDMT) [39], [40], and in several registry studies [36], [63]–[65]. Compared to conventional mitral valve surgery, MitraClip treatment was less effective at reducing mitral regurgitation; however, MitraClip treatment was associated with fewer major adverse events at 30 days, and demonstrated sustained improvements in quality of life and heart failure symptoms [12]. Registry data has also demonstrated that while transcatheter repair can be safely performed in patients at prohibitive surgical risk and result in significant MR reduction, rates of death and heart failure hospitalization following treatment with MitraClip remain higher in patients with secondary MR than primary MR [36].

The outcomes from the Cardiovascular Outcomes Assessment of the Percutaneous Therapy for Heart Failure Patients with Functional Mitral Regurgitation (COAPT) trial were recently published, which compared MitraClip + GDMT to GDMT alone in patients with moderate-to-severe or severe secondary MR [40]. The outcomes showed that MitraClip repair resulted in a significantly greater number of patients with sustained reduction of MR to Grade  $\leq 2+$  ( $p < 0.004$ ), significantly improved quality of life (KCCQ;  $p < 0.001$ ) and functional capacity (NYHA Class I/II;  $p < 0.001$ ) at 12-months compared to GDMT treatment alone. At 24 months of follow-up, the MitraClip group also had a lower rate of hospitalization for heart failure ( $p < 0.001$ ), and lower mortality ( $p < 0.001$ ) versus GDMT treatment alone. These outcomes strongly suggest that there is a significant clinical benefit from transcatheter intervention in patients with severe secondary MR who may not be candidates for surgery.

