### ***2.1.6 Transcatheter Mitral Valve Replacement***

Transcatheter mitral valve replacement (TMVR) has recently emerged as an exciting new frontier in the field of cardiac structural interventions. Although transcatheter aortic valve replacement (TAVR) is a well-established treatment option for patients with symptomatic severe calcific aortic stenosis, the experience with transcatheter mitral valve implantation remains at an earlier stage.

There have been important challenges in the development of this technology, including the complexity of the mitral valve anatomy involving a saddle-shaped elliptical annulus, the subvalvular apparatus, the interaction with the left ventricular outflow tract (LVOT) and the aortic valve, as well as the large size of TMVR devices and catheters for implantation [67].

Furthermore, the patients being considered for TMVR are usually high risk with multiple comorbidities, including frailty, pulmonary hypertension, or severe left ventricular systolic dysfunction, each of which negatively impact the overall clinical outcome. Despite these technical, anatomic, and clinical limitations, there has been significant progress in recent years.

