### ***2.1.7 Clinical Experience with the Tendyne Transcatheter Mitral Valve System***

The Expanded Clinical Study of the Tendyne Transcatheter Mitral Valve System (NCT02321514), prospectively evaluated the use of the Tendyne Transcatheter Mitral Valve System, deployed using a transapical approach without cardiopulmonary bypass, in patients with severe native valve MR. The results of the first 30 patients through 30-day follow-up as well as the results of the first 100 patients through 1-year follow-up have been published in the Journal of the American College of Cardiology [68], [69].

The first 100 patients were enrolled between November 2014 and November 2017 at 24 sites (3 in Australia, 8 in Europe, and 13 in the United States) [69]. The MR etiology for these patients was secondary or mixed in 89 subjects, and primary in 11. The Tendyne Transcatheter Mitral Valve System had a high implantation success rate (97%) and a low procedural adverse event rate, with no operative deaths, strokes, or conversions to open heart surgery.

TTE at one-month follow-up showed no more than trace residual MR in 98.8% of patients, and 98.4% of patients having trace or less MR at one year, demonstrating sustained MR elimination. The majority (88.5%) of surviving patients reported mild or no symptoms at one-year follow-up (NYHA Class I or II). Improved quality of life was also observed, where 73.4% of surviving patients had >10-point improvement in their Kansas City Cardiomyopathy Questionnaire score.

The Tendyne Transcatheter Mitral Valve System has also been successfully implanted in nine patients with severe MAC under compassionate use [70]. Device implantation with complete relief of MR occurred in all patients, and there were no instances of device embolization, significant mitral stenosis, or need for cardiopulmonary bypass or hemodynamic support. Technical success was achieved in eight of the nine patients.

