### **Screening Assessments within 90 Days Prior to Registration**

Subjects must complete all trial required assessments prior to registration in the randomized cohort and prior to the procedure in roll-in subjects and the non-repairable or severe MAC cohorts.

- Medical history must be obtained, including review of subject's medical records. This review will include history of comorbidities and pre-existing medical conditions; previous cardiovascular and peripheral vascular interventions; symptoms and diagnosis of mitral insufficiency; history of hospitalizations (related to heart failure and mitral valve insufficiency) within the past 12 months.
- A physical exam including an assessment of subject's cardiac status and sitting vital signs (heart rate and blood pressure).
- Blood tests performed, including: BNP or NT-proBNP, plasma free hemoglobin, serum creatinine, serum albumin, International Normalized Ratio (INR), Creatine kinase-MB (CK-MB) if indicated or Troponin (Type I or T) if indicated.
- A 12-lead electrocardiogram (ECG) must be performed.
- Concomitant chronic cardiovascular medications must be documented and may include the following: anticoagulants, antiplatelet agents, ACE inhibitors, angiotensin II receptor blockers or inhibitors, angiotensin receptor-neprilysin inhibitor, If channel inhibitor, beta

blockers, calcium channel blockers, diuretics, digitalis preparations, and any medication that may increase the risk of bleeding.

- Modified Rankin Scale must be assessed.
- NYHA Functional Classification must be assessed.
- Canadian Cardiovascular Society (CCS) grading of angina pectoris must be assessed.
- KCCQ, SF-12, and EQ-5D questionnaires must be completed by the subject;
  - **Note:** To minimize bias and undue influence, the QoL questionnaires will be completed by the subject, unless the subject is unable to complete the questionnaire on their own (in such cases a note to file must be completed to document the inability of subject to complete the questionnaire on their own).
- The 6MWT must be administered according to the ATS Statement [77]
- The following assessments will be captured to assist the local site heart team and SEC in determining a subject's risk profile. These assessments include, but are not limited to:
  - STS Predicted Risk of Mortality (PROM) score for both mitral valve replacement and repair
  - Essential Frailty Toolset (see
  - Appendix V: Essential Frailty Toolset

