2.2.3 Survival Analyses

Survival analysis will be conducted to analyze time-to-event variables. Subjects without events will be censored at their last known event-free time point when they stay in the study. Survival curves will be constructed using Kaplan-Meier estimates.

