2.3.1.2.2 Freedom from all-cause mortality and MV reintervention at 12 months

The Tendyne device may reduce the risk for surgical reintervention and subjects in the Treatment group are expected to experience greater reduction in MR severity than subjects in the Control group. The proportion of subjects alive and without MV reintervention at 12 months will be compared between the Treatment and Control groups.

The null and alternative hypotheses are stated as:

$$H_0: \pi_D - \pi_C \leq -d$$

$$H_1: \pi_D - \pi_C > -d$$

where π_D and π_C are the true event rates for the composite of freedom from all-cause mortality and MV reintervention at 12 months in the Treatment and Control group, respectively, and d is the non-inferiority margin of 10%.

using a one-sided test with a 2.5% significance level, as described above in [Section 2.3.1.1](#).

2.3.1.2.3 Improvement in KCCQ by at least 10 points at 12 months from baseline

To evaluate the benefit of the Tendyne device, the improvement in Quality of Life as measured by change in the KCCQ scores at 12 months from baseline will be compared between the Treatment and Control

Statistical Analysis Plan

groups.

The null and alternative hypotheses are stated as:

$$H_0: P_D - P_C \leq -d$$

$$H_1: P_D - P_C > -d$$

where P_D and P_C represent the proportion of subjects who improve at least 10 points in KCCQ score at 12 months from baseline in the Treatment and Control groups, respectively, and d is the non-inferiority margin of 15%. [REDACTED]

[REDACTED]

[REDACTED]

2.3.1.2.4 Proportion of Patients with NYHA Functional Classification I or II at 12 months

To evaluate improvement in heart failure symptoms, the proportion of NYHA Functional Classification I or II at 12 months will be compared with that at baseline.

The null and alternative hypotheses are stated as:

$$H_0: P_D - P_C \leq -d$$

$$H_1: P_D - P_C > -d$$

where P_D and P_C represent the proportion of subjects with NYHA Classification I/II at 12 months for treatment and control, respectively, and d is the non-inferiority margin of 15%. [REDACTED]

[REDACTED]

[REDACTED]

2.3.1.2.5 Improvement in Six-Minute Walk Test Distance by at least 50 meters at 12 months from baseline

To evaluate the benefit of the Tendyne device, the increase in the Six-Minute Walk Test distance will be compared between the Treatment and Control groups.

The null and alternative hypotheses are stated as:

$$H_0: P_D - P_C \leq -d$$

$$H_1: P_D - P_C > -d$$

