3.0 DESCRIPTIVE ENDPOINTS AND ADDITIONAL DATA

3.1 Baseline and Demographic Characteristics

The following baseline and demographic variables will be summarized for the subjects enrolled: gender, age, ethnicity, race, height, weight, medical history, health status, quality of life, functionality, MR classification and quantification, echocardiographic measures, medications, etc.

Statistical Analysis Plan

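### SAP 2.12 makes the unadjusted analysis the default; prespecifying a covariate-standardized primary comparison in the Randomized cohort would be a cheap, modest gain in precision, not the correction of an error

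*SAP*

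**What the plan says.** SAP 2.12 sets the rule for the whole plan: "Unless otherwise specified, no adjustments for covariates will be made for any of the variables in the analysis". The opening words allow exceptions, but none is readable for the Randomized cohort. SAP 2.3.1.1 to 2.3.1.2.5 state every hypothesis as a plain difference in rates or proportions. SAP 2.2.2 and 2.2.3 describe differences in proportions and Kaplan-Meier estimates, with this censoring rule: "Subjects without events will be censored at their last known event-free time point when they stay in the study".

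Baseline data appear in SAP 3.1 ("The following baseline and demographic variables will be summarized for the subjects enrolled"), as subgroup factors in SAP 2.8, and inside change scores. For KCCQ, SAP 2.3.1.2.3 compares "the proportion of subjects who improve at least 10 points in KCCQ score at 12 months", so the baseline value is part of the outcome definition.

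Protocol 6.1.2 requires NYHA class, KCCQ and the 6-minute walk before registration, and also "STS Predicted Risk of Mortality (PROM) score for both mitral valve replacement and repair". LVEF is measured at screening (Protocol 5.2.3). Randomization is stratified by site only (SAP 1.3).

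**The concern.** The Randomized cohort succeeds or fails on one non-inferiority test: margin 12.5 points, one-sided 5%, about 382 subjects, no interim analysis. The result turns on the lower confidence limit of the 12-month difference, so any variance that baseline data could remove bears on it.

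The Protocol itself describes some baselines as prognostic. Section 2.1.6 lists comorbidities of TMVR candidates, "including frailty, pulmonary hypertension, or severe left ventricular systolic dysfunction, each of which negatively impact the overall clinical outcome". Section 2.1.5 reports that "rates of death and heart failure hospitalization following treatment with MitraClip remain higher in patients with secondary MR than primary MR". Both give a direction and neither gives a strength. As far as can be read, this information is left out of the comparison. An adjusted estimate of the same marginal difference could narrow the limit without changing the estimand or the margin.

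**Working it through.** **Inputs from the documents.** 382 subjects randomized 1:1, so 191 per arm (SAP 1.3, 1.5.1); margin 12.5 points and one-sided 5% (SAP 2.3.1.1); margin 15 points for the responder endpoints (SAP 2.3.1.2.3, 2.3.1.2.5), at one-sided 2.5% (Protocol 10.2.1).

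**Assumptions.** 60% event-free in both arms; R² (share of outcome variance explained by baselines) of 2–15%. Neither is readable.

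**The plan's own figure.** The event rates, power and dropout behind 382 are redacted, so it cannot be reproduced. It is plausible: with no dropout, a 60% rate needs 380 for 80% power and a 70% rate needs 388 for 85%.

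**Primary endpoint.** SE = √(2 × 0.6 × 0.4 / 191) = 0.0501. Adjustment multiplies it by √(1 − R²). Power = Φ(0.125/SE − 1.645). The largest observed Tendyne deficit that still passes is 12.5 − 100 × 1.645 × SE points.

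| R² | Power | Largest passing deficit (points) | Equivalent N = 382/(1 − R²) |
|---|---|---|---|
| 0 | 80.2% | 4.25 | 382 |
| 2% | 80.9% | 4.34 | 390 |
| 5% | 82.0% | 4.46 | 402 |
| 10% | 83.7% | 4.68 | 424 |
| 15% | 85.5% | 4.90 | 449 |

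Over R² of 2–15%, a 50% event-free rate takes power from 78.8% to 79.5–84.3%, and a 70% rate from 84.6% to 85.3–89.4%.

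**Why the low end is better supported.** Eligibility narrows some covariates. LVEF below 25% is excluded (Protocol 5.2.3), and the MitraClip indication for secondary MR caps it at 50% (Protocol Appendix X). If the covariate SD falls to a fraction u = 0.7–0.9 (assumed), R² becomes R²u²/(1 − R² + R²u²). Then 5%, 10% and 15% shrink to 2.5–4.1%, 5.2–8.3% and 8.0–12.5%, with power 81.1–81.6%, 82.0–83.1% and 83.0–84.6%.

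MR etiology alone adds little. Protocol 2.1.7 reports, for an earlier Tendyne study, "The MR etiology for these patients was secondary or mixed in 89 subjects, and primary in 11". With q = 0.11 and an assumed event-free gap of 10 or 20 points, R² = q(1 − q) × gap²/0.24 = 0.4% or 1.6%, and power is 80.3% or 80.8%.

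**Censored simulation.** 6,000 runs per cell, 191 per arm, exponential times, 10% loss by 12 months. Covariates: MR etiology (11% primary), NYHA III/IV (60%, assumed) and two standardized continuous variables. Log-hazard coefficients in that order: weak (−0.3, 0.3, −0.15, 0.2), moderate (−0.4, 0.4, −0.25, 0.35), stronger (−0.5, 0.5, −0.35, 0.5), giving R² of 3.4%, 8.4% and 14.6%. The Kaplan-Meier difference is compared with pseudo-value regression using robust SEs; missing covariates are mean-filled.

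| Covariates missing | Weak | Moderate | Stronger |
|---|---|---|---|
| 0% | 77.9 → 78.8% | 78.4 → 81.1% | 78.0 → 82.8% |
| 10% | 78.6 → 79.2% | 78.7 → 80.7% | 77.9 → 81.8% |
| 20% | 78.6 → 78.7% | 78.0 → 79.3% | 78.2 → 82.4% |

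Adjusted type I error was 4.1–5.1% against a nominal 5%. Monte Carlo SE is about 0.5 points for power and 0.3 for size.

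**Validity of the unadjusted test.** A separate binary-outcome simulation (3,000 trials per scenario, one covariate, no censoring) gave unadjusted bias of at most 0.2 points and type I error of 4.3–5.5%.

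**Responder endpoints.** Assumed: 150 evaluable per arm, 60% responders, baseline/12-month correlation r = 0.5–0.8, no multiplicity step. SE = √(2 × 0.24/150) = 0.0566; unadjusted power = Φ(0.15/0.0566 − 1.96) = 75.5%. With s the ratio of 12-month to baseline SD, the squared correlation of change with baseline is (rs − 1)²/(1 + s² − 2rs). R² is that times φ(t)²/(p(1 − p)), where Φ(t) = p = 0.6; the multiplier is 0.386²/0.24 = 0.62.

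| s | Adjusted power, r = 0.8 to 0.5 |
|---|---|
| 0.9 | 81.2–84.5% |
| 1.0 | 78.2–82.3% |
| 1.1 | 76.4–80.4% |
| 1.2 | 75.6–79.0% |

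**The case against.** The strongest case against is that nothing is broken. An unadjusted difference with a stated default is a legitimate prespecified choice. SAP 2.12 allows exceptions, and the places where one would sit (test statistics, subgroup models, missing data, sample-size code, tipping-point appendix) are largely blacked out. This stands: the point can only be a conditional recommendation.

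A reader might infer that the unadjusted test is biased or too lenient, or that the plan omits adjustment altogether. The documents support neither. Randomization protects the comparison, and redacted text is not absent text.

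The size of the gain is assumed throughout, and the Protocol's prognostic statements give direction only. This also stands. The responder gain depends on an SD ratio the documents do not give, and at a ratio of 1.2 with r = 0.8 it is practically nil.

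Two technical objections carry less weight. SAP 2.3 censors at COVID-19-related hospitalization or death, which may depend on baseline risk, whereas ordinary pseudo-values need censoring unrelated to covariates. A check with covariate-dependent censoring nevertheless kept size near 5% with about 7–9% lower variance. Site, the only stratification factor, is missing from the suggested covariates. With up to 80 sites (382/80 ≈ 4.8 subjects each) it does not suit a short list, and ignoring it tends to make the unadjusted test slightly conservative.

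Finally, changing a primary estimator while site and some sponsor staff know assignments (Protocol 12.7) invites questions about prespecification. That is a real cost, and it limits who may make the choice.

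**Conclusion.** The point holds as an efficiency recommendation. SAP 2.12 makes unadjusted analysis the default, and no readable text specifies a covariate-adjusted comparison for the Randomized cohort. The planned test is valid as it stands.

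Under the stated assumptions, prespecified adjustment is worth roughly 1 to 4 points of power for R² of 2–10%. The lower part of that range is the more credible. With weak baselines and 20% of covariate values missing, the simulated gain was 0.1 point. Responder gains run from almost nothing to about 9 points, depending on the SD ratio and correlation, and are not the power of the full multiplicity procedure. Confidence is medium, because event rates, covariate strength and the test statistics cannot be read.

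**What to change.** Unless a redacted section already does so, amend SAP 2.12 for the Randomized cohort before comparative data are examined:

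- Make the primary non-inferiority analysis a covariate-standardized marginal difference in 12-month event-free probability. Use an estimator that handles censoring (pseudo-value regression, for example) and a robust SE, and leave the 12.5% margin unchanged.
- Fix a short list of baselines already collected, such as LVEF, one named STS PROM score (two are recorded), NYHA II versus III/IV, and MR etiology.
- State a missing-covariate rule that keeps every randomized subject, such as the pooled baseline mean, using neither arm nor outcome.
- Adjust the KCCQ and 6MWD responder comparisons for their own baseline values.
- Report the unadjusted results alongside.

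If the unadjusted test stays primary, a prespecified supportive adjusted analysis is still possible, but it would not change the primary verdict or its power.

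The cost is extra SAP wording and modest programming, with no new data. The covariate list, estimator and missing-covariate rule must be settled by people without access to outcomes by arm.
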